## **7.5. Storage and Analysis of Samples**

No samples will be stored. Routine laboratory tests will be undertaken as per clinical practice in an NHS laboratory and samples destroyed after analysis. No additional research specific samples will be taken, the results from routine clinical tests will be used.

## **7.6. End of Study**

The end of study will be defined as when the last 12 month follow-up visits are complete. The CI will notify the Sponsor, participating sites and REC within 90 days of the end of study. The clinical study report will be written within 12 months of the end of study.

## **8. SAFETY REPORTING**

Not applicable

## **9. DATA HANDLING**

### **9.1. System and Compliance**

All data will be collected on a paper CRF for each participant where each participant will be assigned a unique ID. CRFs will be held securely in the renal research office, a locked room with storage cabinets. The electronic results system will be the source document for haematological and biochemical laboratory test results. This will be collated on secure trust server Excel document, which will be password protected. Only study staff shall have access to study documentation other than the regulatory requirements listed below. The investigators will keep records of all participating patients, all original signed informed consent forms and copies of the CRF pages in the Investigator Site File. Data will be added into the CRF directly and therefore it will act as a source document.

### **9.2. Source Data**

Refer to section 9.1

### **9.3. Data Workflow**

The CRF will be managed by the investigatory team and data from the CRF will be entered into an electronic database (excel) by participant ID which will be held will be held securely and password protected. All data will be stored on a secure dedicated web server (University Hospitals of Derby and Burton NHS Foundation Trust). Access will be restricted by user identifiers and passwords (encrypted using a one-way encryption method). Information about the study in the participant's medical records / hospital notes will be treated confidentially in the same way as all other confidential medical information. Electronic data will be backed up every 24 hours to both local and remote media in encrypted format as per the standard server backup process.

#### **9.4. Data Access and Security**

Only the CI and co-investigators will have access to the anonymised data.

Direct access will be granted to authorised representatives from the Sponsor, host institution and the regulatory authorities to permit study-related monitoring, audits and inspections.

#### **9.5. Archiving**

At the end of the study, following completion of the end of study report, UHDB will securely archive all centrally held study related documentation for a minimum of 5 years. At the end of the defined archive period arrangements for confidential destruction will be made. It is the responsibility of each PI to ensure that data and all essential documents relating to the study are retained securely for a minimum of 5 years after the end of study, and in accordance with national legislation.

UHDB will notify sites when study documentation held at sites may be archived and then destroyed. All archived documents must continue to be available for inspection by appropriate authorities upon request.

### **10. STATISTICS AND DATA ANALYSIS**

#### **10.1. Sample Size Calculation**

As prospective cohort study no formal power calculation to determine sample size is required.

#### **10.2. Planned Recruitment Rate**

There are approximately 30 renal transplants per year who return to follow up to UHDB, we aim to recruit over one year. Therefore, the aim is to recruit approximately 25 patients.

#### **10.3. Statistical Analysis**

##### **10.3.1. Summary of Baseline Data and Flow of Patients**

Descriptive statistics will be presented to summarize the distribution of baseline variables across each of the randomisation groups. The continuous baseline variables (age, height, weight and blood pressure, eGFR, BMI) will be reported with means & 95% confidence intervals (95% CI), if shown to be normally distributed, otherwise will be reported with medians & Interquartile Ranges (IQR). The categorical variables (gender, ethnicity, comorbidities) will be reported with frequencies & percentages. We will record and report the numbers lost to follow up and the reasons for this.

### **10.3.2. Outcome Analysis**

We plan to assess the data regarding changes to cardiovascular risk factors initially using visual methods. We will use descriptive statistics across the different time frames. We will compare values for the outcomes for different time points using longitudinal modelling.

For the interviews we will use content analysis to analyse themes within the interviews. Data will be recorded, transcribed and coded by the research team. The data will then be anonymised and stored, accessed, archived and deleted as per section 9 of the protocol.

### **10.3.3 Interim analysis**

We are not planning any interim analysis in this observational study.

### **10.3.4 Analysis groups**

There are no pre-specified groups for analysis.

## **10.4 Procedure(s) to Account for Missing or Spurious Data**

Missing data will be reported as absent given the small sample size and nature of the study. Imputation will not be used.

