## STUDY FLOW CHART

## STUDY PROTOCOL

### 1. BACKGROUND

At the end of 2022 39,874 adult patients in the UK were living with a kidney transplant, representing 56.2% of the population on kidney replacement therapy. Kidney transplant remains the gold standard of renal replacement therapy and confers benefits in survival and quality of life over dialysis. Short term survival post-transplant is good, with 94% adjusted 5 year survival in the UK for a transplant from a living donor and 87% for a deceased donor from the most recent UK renal registry data.

A high proportion of renal transplant patients have a high burden of comorbidities. Increasing multimorbidity has been shown in the general population to increase risk of premature death and hospital admissions and is associated with poorer function and greater economic costs. Much of the data in kidney transplant recipients focusses on comorbidity burden at time of transplant and the predictive use of this data for outcomes. There is little available data on the patterns and progression of multimorbidity for patients living with renal transplant. An assessment of the wider CKD cohort was undertaken using medical records and self reporting to understand multimorbidity, with a group of 176 transplant patients in the UK and showed that 92% had at least one comorbidity in addition to CKD. The most common comorbidity was hypertension (60.1%), followed by musculoskeletal conditions (40.9%) and then cardiovascular disease and diabetes. However, there is no data available, in this study or others, on the longitudinal development of comorbidities after transplant receipt. There is also no data available on the impact of multimorbidity on the quality of life of kidney transplant recipients. Although there is evidence for development of specific conditions, this has not been examined within the context of multiple long term health conditions.

There is no consensus on the measurement of multimorbidity, and no consensus on which comorbid conditions should be used in a count. Expert reviewers suggest the conditions used to define multimorbidity should be guided by health impact and may be tailored to a study population. No such work has taken place in the kidney transplant population.

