#### **3.2. Outcome**

##### **Primary outcomes:**

1. To measure the number and type of comorbidities of patients in the one year post renal transplantation.
2. To measure the cardiovascular risk factors over one year post transplant. (Blood pressure, lipid levels, BMI, HbA1c.).

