## **7.3. Study Assessments**

Data will be collected from medical records, confirmed with participants and entered into the CRF: Participants will have demographic information recorded at baseline. This will include age, primary renal diagnosis, dialysis modality and vintage, and transplant details including deceased or living donor, induction regime, and length of hospital stay for transplant operation.

At each study visit collect the following data: eGFR (using the creatinine-based formula (CKD-EPI)), HbA1c, lipid levels, urine ACR, standardised office blood pressure, weight, height, smoking status, functional status, comorbidities, medications.

Functional status will be assessed using the KDQOL SF 36 and a sit-to-stand test. This is a validated survey assessing quality of life for patients with kidney disease. KDQOL has been translated and validated in a number of languages and if these are available will be used when applicable, along-side translation services in place in the renal department when needed.

For those in group 2 bioimpedance will be done at baseline, 6 months, and one year. Bioimpedance will involve the Inbody bioimpedance machine in the UHDB renal outpatients department. These involves participants wearing light clothing and takes approximately 5 minutes. This measures body composition, which divides weight into different components.

The structured interview will take approximately 20 minutes, and will take place at the closest available outpatient clinic appointment to the one year follow up visit. This will be recorded via already available transcription devices and transcribed by the study team.

Study visits will be aligned to the closest clinic appointment. Study visits will be at the first available opportunity after return to follow up at UHDB, then subsequently at one month, three months, six months and one year after this visit. Blood tests will be taken as part of usual standard of care and data collected from these results resulting in no extra blood tests for the patient.

There will be no compensation for participants. We will offer refreshments for the study assessments from within the department. If a patient requires transport this will be part of their normal clinic arrangements. We discussed the format of the assessments with our local PPIE group who felt that the arrangements were satisfactory.

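### Does reporting missing data as absent (Protocol 10.4) turn an unrecorded comorbidity into a condition the patient does not have?

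*Protocol*

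**What the plan says.** Section 10.4 gives the only missing-data rule, in two sentences. The first is "Missing data will be reported as absent given the small sample size and nature of the study". The second says that no imputation will be done. The rule applies to all data without distinction.

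Section 3.2 lists two primary outcomes. The first is "To measure the number and type of comorbidities of patients in the one year post renal transplantation"; the second covers blood pressure, lipids, BMI and HbA1c.

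Section 10.3.1, on baseline data and patient flow, says "The categorical variables (gender, ethnicity, comorbidities) will be reported with frequencies & percentages". It also commits to reporting how many patients are lost to follow-up, and why.

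Section 10.3.2 opens with "We plan to assess the data regarding changes to cardiovascular risk factors initially using visual methods". It then plans descriptive statistics over time and adds "We will compare values for the outcomes for different time points using longitudinal modelling".

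Section 7.3 gives the data source: "Data will be collected from medical records, confirmed with participants and entered into the CRF". It also ties study visits to the nearest clinic appointment.

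**The concern.** For a laboratory value, absent has one meaning. For a comorbidity it has two: the value is missing, or the patient does not have the condition. On the second meaning, a patient with no record at a visit would be counted as free of every condition. The error would always run downwards and would grow as visits are missed. It would fall on the primary aim, change in multimorbidity over the year: a true rise could be hidden, or a fall could appear where nobody had changed.

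A second worry is coverage. Section 10.3.2 begins with cardiovascular risk factors and never names the comorbidity count. If the longitudinal model left the count out, the first primary outcome would rest on crude summaries per visit, and those can understate a rise if sicker patients are the ones who miss visits.

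**Working it through.** The protocol states no figure on this point, so there is nothing to reproduce. The check has two parts: how large the error would be on the adverse reading, and which reading the text supports.

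**Size on the adverse reading**

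Inputs:
- Prevalences from Section 1: "92% had at least one comorbidity in addition to CKD", and hypertension in 60.1%. They come from an earlier UK cohort and serve only as illustration.
- Sample size: about 25 (Section 10.2) or 30 (Study Summary).
- Patients missing at a visit, k: assumed to be 1, 3 or 5, because the protocol gives no rate. Missingness is assumed unrelated to comorbidity.

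Formula if gaps are scored as not present: shown prevalence = p × (N − k)/N.

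| N | k | 92% appears as | 60.1% appears as |
|---|---|---|---|
| 25 | 1 | 0.92 × 24/25 = 88.3% | 0.601 × 24/25 = 57.7% |
| 25 | 3 | 0.92 × 22/25 = 81.0% | 0.601 × 22/25 = 52.9% |
| 25 | 5 | 0.92 × 20/25 = 73.6% | 0.601 × 20/25 = 48.1% |
| 30 | 3 | 0.92 × 27/30 = 82.8% | 0.601 × 27/30 = 54.1% |

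If gaps are left as missing, the expected prevalences remain 92% and 60.1% under the same assumption.

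A whole-number case shows where the two codings part. Let 23 of 25 patients (92%) have at least one condition, and let 3 of those 23 miss a visit. Scored as not present, the result is 20/25 = 80%. Left as missing, it is 20/22 = 90.9%. The numerator is 20 both times; only the denominator differs.

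**Which reading the text supports**

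1. The second sentence of 10.4 excludes imputation. Replacing an unknown status by no is imputation with a fixed value, so on the adverse reading the two sentences of the section would contradict each other. On the reading that a gap is shown as a gap, they agree.
2. One rule covers every variable. For blood pressure, lipids, HbA1c, eGFR or the quality-of-life score, absent can only mean no value. A single sentence should carry a single meaning.
3. The reason given is the small sample. That explains why nothing is imputed; it gives no ground for scoring gaps as no.
4. The percentages in 10.3.1 are for baseline variables, whereas the feared false fall would arise at follow-up. The same section has losses reported with reasons, so patients who leave would be visible as lost.
5. Under 7.3, comorbidity data start from the medical record. A missed visit need not leave status unknown. To reach 81.0%, staff would have to enter no conditions for patients whose conditions already stand in the notes and in earlier CRF pages.

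**Coverage of the model**

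The modelling sentence in 10.3.2 refers to the outcomes without restriction, and the comorbidity outcome is the first one listed in 3.2. The plain reading includes it. The model family for a count, and whether all available visits are used, are commonly settled in a statistical analysis plan, which is not at hand.

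**The case for a change.** The strongest case for a change is practical. Data pass from a paper CRF into an Excel sheet (Sections 9.1 and 9.3). Someone facing a blank comorbidity cell may enter no without thinking of it as imputation, and the literal wording of 10.4 does not stop them. Incomplete series are foreseeable, since data from withdrawn participants may still be used (Section 7.4). The error would hit the primary outcome in one direction, at 92/25 = 3.7 points per missing patient for at least one comorbidity and 60.1/25 = 2.4 points for hypertension. Clearer wording would cost a sentence.

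What stands is that the word is badly chosen beside a present/absent outcome, and that the arithmetic is right on its assumptions. What does not stand is that the plan leads there. The harm needs a reading that the next sentence excludes, together with staff who disregard the record they are told to work from. The remaining point, that sicker patients may miss more visits, applies to crude summaries in any cohort. The documents give no figure for it, and the planned longitudinal modelling largely deals with it if it is likelihood-based and uses all available visits. Completing missed visits from the record would add little, because the record is already the source.

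**Conclusion.** No change to the plan follows. Section 10.4 is loosely worded, but read with its own second sentence and across all the variables it governs, it means that missing values are shown as missing and not filled in. On that reading the expected distortion is zero, provided missingness is unrelated to comorbidity. The drop from 92% to 81.0%, or from 60.1% to 52.9%, arises only on the excluded reading and with an assumed 3 of 25 patients missing. Section 10.3.2 covers the comorbidity count on its plain wording, and the detail of the model may properly sit in an analysis plan. In a small exploratory, descriptive study this is a matter of word choice that an analyst would resolve correctly; following the protocol as written does not give a wrong result.

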## **11. MONITORING, AUDIT & INSPECTION**

The Investigator(s) must ensure that source documents and other documentation for this study are made available to study monitors, the REC or regulatory authority inspectors. Authorised representatives of the Sponsor may visit the participating sites to conduct audits/ inspections.

Monitoring and source data verification will be conducted by the Sponsor according to the study monitoring plan. The extent and nature of monitoring will be determined by the study objectives, purpose, design, complexity, blinding, number of patients and sites, and endpoints.

## **12. ETHICAL AND REGULATORY CONSIDERATIONS**

### **12.1. Assessment and Management of Risk**

The risks associated with the study are low as no treatment invention is proposed. Participants who will be having body composition assessed with BIA will be screened to ensure they do not have a pacemaker prior, which is an exclusion criteria to this area of the study due to possible electromagnetic interference. Participants will be encouraged to discuss any concerns about venepuncture for laboratory tests when consenting for the study. This is to allow minimalizing venepuncture where possible (for instance checking study tests with the required clinic visit bloods for CKD monitoring at the same time).

## **12.2. Public and Patient Involvement**

This study was discussed with the renal departments public and patient involvement group, who commented that they thought that this area of research was a 'really good idea'. They felt the proposed visits were 'for most people it won't feel like more than the loving care and attention they normally get'.

They commented on weight gain after transplant and the impact of health burden on their quality of life, and felt a study assessing some of these issues would be beneficial.

Previous PPIE meetings on similar study designs in our department have identified clinic visits as a convenient time to conduct research visits. Usually, clinic visits in nephrology involve observations check with the nursing team, followed by clinician review, possible dietitian review and finally venepuncture. Integrating study discussion and visit in this session would allow participation without another trip to hospital.

PPIE will continue throughout all stages of the study in the Derby Renal Research Patient and Public Involvement group meetings. PPIE representatives will also be involved at the point of dissemination. Patient representatives will be supported to report the findings of the study and the experience of their involvement in patient publications and on patient and public-facing websites and invited to participate in conference presentations.

## **12.3. Research Ethics Committee (REC) & Regulatory Considerations**

The study will be conducted in compliance with the approved protocol and the Declaration of Helsinki. The protocol and all related documentation (e.g. informed consent form, participant information sheet, questionnaires) have been reviewed and received approval by a Research Ethics Committee (REC). The investigator will not begin any participant activities until approval from the HRA and REC has been obtained and documented. All documentation and correspondence must be retained in the trial master file/investigator site file. Substantial amendments that require HRA and REC (where applicable) review will not be implemented until the HRA and REC grants a favourable opinion (with the exception of those necessary to reduce immediate risk to participants).

It is the responsibility of the CI to ensure that an annual progress report (APR) is submitted to the REC within 30 days of the anniversary date on which the favourable opinion was given, annually until the study is declared ended. The CI is also responsible for notifying the REC of the end of study (see Section 6.9) within 90 days. Within one year of the end of study, the CI will submit a final report with the results, including any publications/abstracts to the REC.

Before any site can enrol a patient into the study confirmation of capacity must be sought from the site's research and development (R&D) department. In addition, for any amendment that will potentially affect the site's permission, the research team must confirm with the site's R&D department that permission is ongoing (Section 12.9).

#### **12.4. Protocol Compliance / Non-compliance Reporting**

The investigator is responsible for ensuring that the study is conducted in accordance with the procedures described in this protocol. Prospective, planned deviations and/or waivers to the protocol are not acceptable, however accidental protocol deviations (non-compliances) may happen and as such these must be recorded. Non-compliances should be recorded in the CRF and/or a non-compliance log kept in the ISF. All non-compliances should be reviewed and assessed by the PI (or appropriately delegated individual) to determine if they meet the criteria of a “serious breach” (Section 12.6). Non-compliances which are found to frequently recur are not acceptable, will require immediate action, and could potentially be classified as a serious breach.

#### **12.5. Notification of Serious Breaches to GCP and/or the Protocol**

A “serious breach” is a departure from the protocol, Sponsor procedures (i.e. SOPs), or regulatory requirements which is likely to effect to a significant degree –

- (a) The safety or physical or mental integrity of the subjects of the study; or
- (b) The scientific value of the study.

If the PI (or delegate) is unsure if a non-compliance meets these criteria, they should consult the Sponsor for further guidance.

If a serious breach is identified the investigator should notify the Sponsor immediately (i.e. within 1 working day) using the ‘Non-CTIMP Notification of a Serious Breach’ form. The report will be reviewed by the Sponsor and CI, and where appropriate, the Sponsor will notify the REC within 7 calendar days of being made aware of the breach.

#### **12.6. Data Protection and Patient Confidentiality**

The study will be conducted in accordance with the Data Protection Act 2018. The investigator must ensure that participant’s anonymity is maintained throughout the study and following completion of the study. Participants will be identified on all study specific documents (except for the informed consent form and enrolment log) only by the participants study specific identifier (and initials if deemed necessary). This identifier will be recorded on documents, biological samples and the database. The Investigator Site File will hold an enrolment log detailing the study specific identifier alongside the names of all participants enrolled in the study.

All documents will be stored securely with access restricted to study staff and authorised personnel.

[name] will act as the custodian of the data generated in the study.

